10.2. Appendix 2: Time & Events

10.2.1. Protocol Defined Time & Events

Table 9 Time and Events Table

Procedures	Pre-screen ¹	Screen Run-in	Treatment (visit window is ± 7 days)									Exit Visit/ Early withdrawal Visit ³
Visit	0	1	2	3	4	5	6	7	8	9	10	
Week	-6 to -4	-4 to -1	0	4	8	12	16	20	24	28	4 weeks post last dose ± 7 days	
Informed Consent ²	x											
Subject Demography	x											
Medical History		x										
Asthma History (including triggers)	x	x										
Therapy History ⁴		x										
Smoking History		x										
Cardiovascular History/Risk Factors		x										
Inclusion/Exclusion Criteria		x										
Continuation to treatment Criteria			x									
Efficacy Assessments⁵												
ACQ-5		x	x	x	x	x	x	x	x	x	x	
Exacerbation review	x	x	x	x	x	x	x	x	x	x	x	
Spirometry including pre- and post bronchodilator FEV ₁ , FVC ⁶		x	x			x			x		x	
Health Outcome Assessments⁵												
SGRQ			x			x			x		x	

Procedures	Pre-screen ¹	Screen Run-in	Treatment (visit window is ± 7 days)									Exit Visit/ Early withdrawal Visit ³
Visit	0	1	2	3	4	5	6	7	8	9	10	
Week	-6 to -4	-4 to -1	0	4	8	12	16	20	24	28	4 weeks post last dose ± 7 days	
Clinician & Subject rated response to therapy				x		x		x			x	
Treatment Satisfaction with Medication Questionnaire (TSQM-9)		x									x	
Exit Interview ⁷											x	
Safety Assessments⁵												
Concomitant Medication	x	x	x	x	x	x	x	x	x	x	x	
Physical Examination, including nasal exam		x										x
Vital Signs		x	x	x	x	x	x	x	x	x	x	
12 lead ECG		x				x						x
Adverse Events		x	x	x	x	x	x	x	x	x	x	
Serious Adverse Events	x	x	x	x	x	x	x	x	x	x	x	
Laboratory Assessments⁵												
Haematology with differential		x	x	x	x	x	x	x	x	x	x	
Clinical Chemistry (incl. LFT)		x	x	x	x	x			x		x	
Parasitic Screening ⁸		x										
Pharmacogenetic sample ⁹							x					
Pregnancy test ¹⁰		U	U	U	U	U	U	U	U	U	U	
HBsAg and hepatitis C antibody ¹¹		x										
Immunogenicity sample			x			x				x	x	
Biomarker sample		x	x		x						x	

Procedures	Pre-screen ¹	Screen Run-in	Treatment (visit window is ± 7 days)									Exit Visit/ Early withdrawal Visit ³
Visit	0	1	2	3	4	5	6	7	8	9	10	
Week	-6 to -4	-4 to -1	0	4	8	12	16	20	24	28	4 weeks post last dose ± 7 days	
Investigational product (Mepolizumab) and rescue medication												
Administer mepolizumab. Contact RAMOS NG to register dispensing visit.			x	x	x	x	x	x	x	x		
Albuterol/salbutamol dispensed (as needed)		x	x	x	x	x	x	x	x	x		
Collect dispensed albuterol/salbutamol			x	x	x	x	x	x	x	x	x	
eCRF/ paper diary/worksheet												
Complete eCRF	x	x	x	x	x	x	x	x	x	x	x	
Dispense paper diary/worksheet	x	x	x	x	x	x	x	x	x	x		
Collect/review paper diary/worksheet		x	x	x	x	x	x	x	x	x	x	
1. Pre-screen Visit 0 must be completed prior to Visit 1 (Screening). It can be completed on the same day as Visit 1 or at up to 2 weeks prior to Visit 1. 2. Subjects will be assigned a subject number at the time ICF signed. The ICF must be signed before any study procedures including medication wash out period(s). 3. Exit Visit may be completed 3 to 5 weeks post last dose. 4. Therapy history to include a detailed review of prior biologics received for treatment of asthma, including omalizumab dose and regimen and prior investigational therapies e.g anti-IL5 or anti-IL13 preparations. 5. All study efficacy, safety and all patient reported questionnaires must be completed prior any study procedure. 6. Spirometry to include pre- and post bronchodilator FEV1 from V2. 7. Exit interview will be conducted only in a subset of sites and in a subset of subjects who choose to participate in the Exit interview. Subjects must be consented prior to interview 8. Parasitic screening is only required in countries with high-risk or for subjects who have visited high-risk countries in the past 6 months. Sites should use local laboratories. 9. Pharmacogenetic sample may be drawn at Visit 2 or any at any visit after. 10. Pregnancy test, U= urine 11. Hepatitis B Surface Antigen and Hepatitis C antibody. (if hepatitis C antibody is positive, hepatitis C will be confirmed by PCR)												

10.3. Appendix 3: Assessment Windows & Visit Slotting

10.3.1. Assessment Windows

Clinic visits are scheduled to take place as specified in [Appendix 2: Time & Events](#). Measurements outside visit windows will not be excluded from analyses. For all clinic visits, nominal visit days and times will be used for reporting, such that if a subject recorded values that were outside of the ± 7 day window for a visit they will still be reported under that visit.

10.3.2. Early Withdrawal / Treatment Discontinuation Visits

If a subject withdraws from the study at a scheduled visit (i.e. completes an Early Withdrawal or Treatment Discontinuation Visit), where endpoint data were scheduled to be collected, the data will be summarised and analysed (as appropriate) together with data from subjects who did not withdraw from the study. If a subject withdraws from the study at a scheduled visit at which endpoint data were not scheduled to be collected, or if a subject withdraws between scheduled visits, data will be slotted to the nearest adjacent visit where the endpoint data was scheduled to be collected (if data at that visit were not recorded) according to the Time and Events schedule ([Appendix 2: Time & Events](#)).

For example, if a subject prematurely withdraws from the study and completed the Early Withdrawal Visit at Visit 6 (Week 16) and completes an Early Withdrawal Visit which includes an FEV₁ assessment, the FEV₁ data collected will need to be re-assigned to an adjacent visit where FEV₁ data is scheduled for collection. In this case the FEV₁ data will be reassigned to Visit 5 (Week 12) (if data at that visit were not recorded) as this is the closest nominal visit at which collection of FEV₁ data is scheduled.

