10.3.3. Unscheduled Visits

For unscheduled visits, similar logic will be applied. If a subject has an unscheduled assessment then this data would be slotted to the closest adjacent scheduled visit but only if information already exists at that visit. If an unscheduled visit occurred between two scheduled visits for which data has been reported, then the data from the unscheduled visit will remain in the unscheduled visit and will not be used in summary tables and analyses (except for endpoints using any post-baseline data) but will be presented in any relevant listings.

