
 When possible unscheduled assessments will be slotted to the closest adjacent scheduled visit. If an unscheduled visit occurs between two completed scheduled visits, the data from the unscheduled visit will not be used in summary tables which are based on by-visit assessments. The information from the unscheduled visit will be included in 'any time post-baseline' summaries and will also be presented in any relevant listings. See Section 10.3 for further details. 	
Descriptive Summary Statistics	
Continuous Data	Refer to IDSL Statistical Principle 6.06.1
Categorical Data	N (number of subjects in the treatment group), n (number of subjects with

Reporting Standards	
	non-missing values), frequency, %
Graphical Displays	
•	Refer to IDSL Statistical Principals 7.01 to 7.13.

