10.6. Appendix 6: Derived and Transformed Data

10.6.1. General

Multiple Measurements at One Time Point

 There are no scheduled multiple measurements, however, if multiple measurements are recorded at a given time point the following process will be followed, unless a process for selection of the measurement for the visit is specified: Mean of the measurements will be calculated and used in any derivation of summary statistics but if listed, all data will be presented. Subjects having both High and Low values for Normal Ranges at any post-baseline visits for safety parameters will be counted in both the High and Low categories of "Any visit post-baseline" row of related summary tables.
Study Day

 Calculated as the number of days from date of first dose of mepolizumab: 
 Ref Date = Missing → Study Day = Missing Ref Date < Date of first dose of mepolizumab → Study Day = Ref Date – Date of first dose of mepolizumab Ref Date ≥ Date of first dose of mepolizumab → Study Day = Ref Date – (Date of first dose of mepolizumab) + 1

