10.7. Appendix 7: Premature Withdrawals & Handling of Missing Data

10.7.1. Premature Withdrawals

Element	Reporting Detail
General	
 A subject will be considered to have completed study treatment if he/she receives study treatment at Visit 9 (Week 28) and completes the Visit 10/Exit Visit (Week 32). A subject will be considered to have completed the study if they continue to participate in the study until the Exit Visit assessments have been completed (regardless of whether the subject completed the study treatment schedule). Subjects who discontinue study treatment or withdraw early will not be replaced in the study. The number of subjects who discontinue study treatment or withdraw early will be summarised and listed. All available data from subjects who were withdrawn from the study will be listed and all available data up to and including the date of early withdrawal will be included in summary tables and figures, unless otherwise specified.
Pre-Screen Failures, Screen Failures and Run-in Failures	
For the purposes of this study pre-screen failures, screen failures and run-in failures will be defined as follows:
 
 Subjects will be assigned a study number at the time of signing the informed consent (Pre-screen Visit). Subjects who do not progress to the Screening Visit will be deemed a pre-screen failure. Those subjects that complete at least one additional Visit 1 (Screening) procedure but do not enter the run-in period will be designated as screen failures. Those subjects that enter the run-in but do not subsequently receive study treatment will be designated as run-in failures.

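### The SAP's slotting condition for unscheduled visits is reversed, and its early-withdrawal rule leaves some SGRQ and FEV1 values with no visit at which to be analysed

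*SAP*

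**What the plan says.** **Early withdrawal (SAP 10.3.2).** If the endpoint was due at the visit where the subject withdraws, "the data will be summarised and analysed (as appropriate) together with data from subjects who did not withdraw from the study". If it was not due, or the subject withdraws between visits, the data are "slotted to the nearest adjacent visit where the endpoint data was scheduled to be collected (if data at that visit were not recorded"). The worked example is a withdrawal visit at Week 16: "In this case the FEV₁ data will be reassigned to Visit 5 (Week 12) (if data at that visit were not recorded"). The section does not say what happens when Week 12 was recorded.

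**Unscheduled visits (SAP 10.3.3 and 10.5.3).** Section 10.3.3 claims to follow the same logic, but has the data "slotted to the closest adjacent scheduled visit but only if information already exists at that visit". It continues: "If an unscheduled visit occurred between two scheduled visits for which data has been reported, then the data from the unscheduled visit will remain" where it was taken; such values are kept out of by-visit summaries and analyses. Section 10.5.3 restates the rule: "When possible unscheduled assessments will be slotted to the closest adjacent scheduled visit". It makes the same exception for a visit between two completed ones and does not require existing data.

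**Several values at one time point (SAP 10.6.1).** "Mean of the measurements will be calculated and used in any derivation of summary statistics", unless a selection process is specified.

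**Inclusion rules.** Section 10.7.1 says of withdrawn subjects that "all available data up to and including the date of early withdrawal will be included in summary tables and figures, unless otherwise specified". Section 7.1.2, to which the SGRQ and FEV1 analyses in 8.1.2 refer, includes all data to Week 32, on or off treatment.

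**The concern.** Slotting rules are programmed as written. A reversed condition in 10.3.3 would be programmed reversed: an unscheduled value taken near a missed visit would stay unused, while one taken near a completed visit could be averaged into it.

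The gap in 10.3.2 matters for endpoints that are not collected at every visit. The models for SGRQ and FEV1 fit nominal visit as a categorical and repeated factor with an unstructured covariance, so a value without a nominal visit cannot enter. If the nearest scheduled visit is already filled, the subject's last SGRQ or FEV1 value has nowhere to go. This conflicts with the all-data rule in 7.1.2. SGRQ at Week 32 is a secondary endpoint and FEV1 is listed among the other endpoints.

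**Working it through.** **1. Unscheduled visits.** Take an unscheduled value and ask whether its closest scheduled visit, and the neighbour on the other side, already have data.

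| Closest visit | Other neighbour | 10.3.3, condition as written | 10.3.3, next sentence | Condition reversed |
|---|---|---|---|---|
| Filled | Filled | Slot | Do not use | Do not slot |
| Filled | Empty | Slot | Silent | Do not slot |
| Empty | Filled | Do not slot | Silent | Slot |
| Empty | Empty | Do not slot | Silent | Slot |

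As written, the condition contradicts the next sentence in the first row and leaves the missed visit empty in the last two. Reversed, it agrees with that sentence, with 10.3.2, and with the exception in 10.5.3. The documents give no number of unscheduled assessments, so this defect cannot be sized. The rule is not limited to any endpoint.

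**2. Withdrawal visits.** Inputs:
- SGRQ is due at Weeks 0, 12, 24 and 32, and so is FEV1 from Visit 2 (SAP Appendix 2).
- The exit visit is 4 weeks after the last dose, with a window of 3 to 5 weeks (same table). Last doses at Weeks 0 to 24 give nominal withdrawal visits at Weeks 4 to 28.
- Protocol 9.2.1 assumes 15% withdrawal: 0.15 × 120 = 18 subjects.
- Assumptions of this check: all earlier visits were attended, withdrawals are spread evenly over the seven times, and every withdrawing subject has an exit visit with the assessment done.

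The SAP's own example first: |16 − 12| = 4 and |16 − 24| = 8, so Week 12 is nearest, as stated. For all seven times:

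| Withdrawal week | Nearest scheduled week | State of that visit | Result under 10.3.2 |
|---|---|---|---|
| 4 | 0 | Filled | No slot if baseline can be a target; otherwise Week 12 |
| 8 | 12 | Empty | Kept |
| 12 | 12 | Own visit | Kept |
| 16 | 12 | Filled | No slot |
| 20 | 24 | Empty | Kept |
| 24 | 24 | Own visit | Kept |
| 28 | 24 or 32 (4 weeks each) | Filled / empty | Undefined |

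Expected subjects without a slot = 18 × (times without a slot) / 7:
- Week 16 only (baseline excluded, tie to Week 32): 18 × 1/7 = 2.6, or 2.1% of 120.
- Two times (baseline allowed and tie to Week 32, or baseline excluded and tie to Week 24): 18 × 2/7 = 5.1, or 4.3%.
- Three times (baseline allowed, tie to Week 24): 18 × 3/7 = 7.7, or 6.4%.

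Letting the exit visit fall evenly over the 3 to 5 week window puts half of the Week 28 visits nearer Week 24. This gives 18 × 2.5/7 = 6.4 with baseline as a target and 18 × 1.5/7 = 3.9 without. ACQ-5 is collected at every visit, and the same calculation gives 0.

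**The case against.** The strongest reply is that 10.3.2 never says a value is dropped. It is silent on the filled case, while 7.1.2 and 10.7.1 say to include the data. That stands: the defect is an undefined case in conflict with the general rules, not a stated deletion. But the general rules do not supply a visit, and 10.7.1 gives way where something else is specified. Section 10.7.1 also promises that withdrawn subjects' data will be listed, yet the planned efficacy listings (10.13.1.7) cover only ACQ-5 and exacerbations. An unslotted SGRQ or FEV1 value would appear in none of them.

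Second, the intended unscheduled rule can be recovered from 10.5.3 and from the second sentence of 10.3.3, and the averaging in 10.6.1 yields to any specified selection process. This makes the slip easy to diagnose, but the text still instructs the opposite.

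Third, 10.5.2.1 defines baseline as the latest assessment before the first dose, so a post-dose value cannot sensibly be slotted there. This is a fair argument for the lower end of the range, though 10.3.2 does not say so.

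A reader might go further and infer that the plan discards the last data of failing subjects and so favours mepolizumab. The documents do not support that. Protocol 5.5.1 lists many reasons for stopping besides lack of efficacy and asks subjects who stop treatment to complete the remaining visits. Nothing shows that the affected values are worse than earlier ones. The reversed sentence governs unscheduled visits and does not cause any loss at withdrawal visits. A reader might also place all 18 withdrawals at the five off-schedule visits and obtain 7 to 11 subjects (18 × 2/5 to 18 × 3/5). That ignores withdrawals at Weeks 12 and 24, which 10.3.2 analyses at their own visit.

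**Conclusion.** Both defects hold, independently of each other. Section 10.3.3 is wrong as written; its effect depends on the number of unscheduled assessments, which the documents do not give. Section 10.3.2 leaves about 5 subjects (2.6 to 7.7, or 2% to 6% of 120) with a last SGRQ and FEV1 value that has no slot, under the even spread and complete exit visits assumed above. Subjects lost to follow-up would have no such value, which would lower the count. The withdrawal gap does not touch the primary ACQ-5 endpoint or blood eosinophils, both collected at every visit, nor exacerbations, which are event-based. No direction of bias in SGRQ or FEV1 is established, and no effect on either estimate has been calculated. The point is worth correcting before database freeze because the text conflicts with itself and the repair is small.

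**What to change.** - **SAP 10.3.3:** change the condition to *only if no information exists at that visit*, so that it agrees with 10.3.2 and 10.5.3. This has no evident downside.
- **SAP 10.3.2:** add that if the nearest scheduled visit already has data, or two scheduled visits are equally near, the value goes to the next empty scheduled post-baseline visit for that endpoint. State that baseline cannot be a target.

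Under the second change every withdrawal value in the table has a slot: Week 4 goes to Week 12, Week 16 to Week 24 and Week 28 to Week 32. The cost is a few sentences and a forward shift of 8, 8 and 4 weeks for those values. The present rule already shifts Weeks 8 and 20 forward by 4 weeks. Protocol 4.4 puts omalizumab wash-out at about 4.5 months, so asthma status may still be changing over an 8-week shift. A footnote to the SGRQ and FEV1 displays should give the number of shifted values.

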10.3.3. Unscheduled Visits

For unscheduled visits, similar logic will be applied. If a subject has an unscheduled assessment then this data would be slotted to the closest adjacent scheduled visit but only if information already exists at that visit. If an unscheduled visit occurred between two scheduled visits for which data has been reported, then the data from the unscheduled visit will remain in the unscheduled visit and will not be used in summary tables and analyses (except for endpoints using any post-baseline data) but will be presented in any relevant listings.

10.4. Appendix 4: Treatment Phases

10.4.1. Treatment Phases (Exacerbations)

Exacerbation data will be classified according to time of occurrence/assessment relative to the first and last date of mepolizumab and the attendance dates of specific visits.

Treatment Phase	Definition
Pre-Treatment	Date & time < First dose of mepolizumab
On-Treatment	Subjects completing treatment and completing the study: First dose of mepolizumab ≤ Date & time ≤ Visit 10 (Exit Visit)* visit date Subjects discontinuing study treatment/withdrawing early from the study: First dose of mepolizumab ≤ Date & time ≤ Earliest of (1) Last dose of mepolizumab + 28 days or (2) Early Withdrawal/Treatment Discontinuation visit date
Off-Treatment	Subjects completing treatment and completing the study: Date & time > Visit 10 (Exit Visit)* visit date Subjects discontinuing study treatment/withdrawing early from the study: Date & time > Earliest of : (1) Last dose of mepolizumab + 28 days or (2) Early Withdrawal/Treatment Discontinuation visit date

* Data may be considered off treatment if beyond acceptable protocol defined limits.

10.4.2. Treatment Phases (Visit Based Efficacy Data)

Efficacy data collected at scheduled visits (including: Questionnaires, PFT, Blood Eosinophils and Biomarkers) will be classified according to time of occurrence/assessment relative to the first and last date of mepolizumab and the attendance dates of specific visits.

Treatment Phase	Definition
Pre-Treatment	Visit date/time ≤ First dose of mepolizumab
On-Treatment	Subjects completing treatment and completing the study: Visit date/time < First dose of mepolizumab ≤ Visit 10 (Exit Visit)* visit date/time Subjects discontinuing study treatment/withdrawing early from the study: Visit date/time < First dose of mepolizumab ≤ Earliest of (1) Last dose of mepolizumab + 28 days or (2) Early Withdrawal/Treatment Discontinuation visit date date/time
Off-Treatment	Subjects completing treatment and completing the study: Date & time > Visit 10 (Exit Visit)* visit date/time Subjects discontinuing study treatment/withdrawing early from the study: Date & time > Earliest of : (1) Last dose of mepolizumab + 28 days or (2) Early Withdrawal/Treatment Discontinuation visit date/time

* Data may be considered off treatment if beyond acceptable protocol defined limits.

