8. SECONDARY STATISTICAL ANALYSES

8.1 Efficacy Analyses

8.1.1. Overview of Planned Efficacy Analyses

The secondary efficacy analyses will be based on the Intent-To-Treat (ITT) population, unless otherwise specified in [Appendix 13: List of Data Displays](#).

[Table 5](#) provides an overview of the planned efficacy analyses, with further details of data displays being presented in [Appendix 13: List of Data Displays](#).

Table 5 Overview of Planned Efficacy Analyses

Endpoint	Absolute ^[1]						Change from Baseline ^{[1] [2]}						
	Stats Analysis			Summary		Individual	Stats Analysis			Summary		Individual	
	T	F	L	T	F	F	L	T	F	L	T	F	F
Secondary Endpoints													
St George's Respiratory Questionnaire (SGRQ)													
On-treatment & Off-treatment	Y			Y				Y	Y		Y	Y	
Blood Eosinophil Count													
On-treatment & Off-treatment	Y			Y				Y	Y		Y		
On-treatment ^[3]	Y							Y					
Other Endpoints													
>= 0.5-point reduction from baseline in ACQ-5 score at Week 32													
On-treatment & Off-treatment										Y	Y		
>= 4-point or greater reduction from baseline in SGRQ Total score at Week 32													
On-treatment & Off-treatment										Y	Y		
Pre-Bronchodilator FEV1													
On-treatment & Off-treatment	Y			Y				Y	Y		Y		
Post-Bronchodilator FEV1													
On-treatment & Off-treatment	Y			Y				Y	Y		Y		
Subject/Clinician Rated Response to Therapy													
On-treatment ^[3]				Y									
Treatment Satisfaction Questionnaire for Medication (TSQM-9)													
On-treatment ^[3]				Y						Y			
Biomarkers													
On-treatment				Y						Y			

Endpoint	Incidence of Events						
	Stats Analysis			Summary		Individual	
	T	F	L	T	F	F	L
Secondary Endpoints							
Clinically Significant Exacerbations							
On-treatment & Off-treatment	Y ^[4]			Y	Y		Y
On-treatment ^[3]	Y ^[4]						
Exacerbations requiring ED visit/hospitalization							
On-treatment & Off-treatment	Y ^[4]			Y			Y
On-treatment ^[3]	Y ^[4]						
Exacerbations requiring hospitalization							
On-treatment & Off-treatment	Y ^[4]			Y			Y

NOTES :

- T = Table, F = Figure, L = Listing, Y = Yes display generated.
- Stats Analysis = Represents TFL related to any formal statistical analyses (i.e. modelling) conducted.
- Summary = Represents TFL related to any summaries (i.e. descriptive statistics) of the observed raw data.
- Individual = Represents FL related to any displays of individual subject observed raw data.

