1. Absolute and change from baseline summaries combined into a single display.
2. Ratio to Baseline to be shown for Blood Eosinophil Count and Biomarker data.
3. To analyse data collected whilst On-Treatment, not considering any data collected following treatment discontinuation (see Section 10.4).
4. Table to include annualised exacerbation rate and 95% confidence intervals from negative binomial model.

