Model Results Presentation

 Adjusted means and the corresponding 95% confidence intervals will be presented by visit. Plots of LS means ratio to baseline in blood eosinophil count and 95% confidence intervals from the model will be generated by visit.
On-treatment Phase

 All subjects in the ITT population will be included within this analysis. All data collected up to and including Week 32 from patients, including those who have discontinued study treatment, will be included in the analysis. An On-Treatment “de jure” analysis will also be performed which does not consider any data collected following treatment discontinuation (see On-Treatment definition within Section 10.4).

Other Statistical Analyses
Other Endpoint

 Percentage of subjects achieving a 0.5-point or greater reduction from baseline in ACQ-5 score at Week 32
Results Presentation

 The number and percentage of subjects achieving a 0.5-point or greater reduction in ACQ-5 Score compared to baseline will be presented for each visit. The number of subjects with a missing ACQ-5 Score at each visit will be presented in a separate category.

On-treatment Phase
• See Primary Efficacy Statistical Analysis, Section 7.1.2

Other Statistical Analyses
Other Endpoint
• Percentage of subjects achieving a 4-point or greater reduction from baseline in SGRQ score at Week 32
Results Presentation

 The number and percentage of subjects achieving a 4-point or greater reduction in SGRQ Total score compared to baseline will be presented for each visit. The number of subjects with a missing SGRQ Total Score at each visit will be presented in a separate category.
On-treatment Phase
• See Primary Efficacy Statistical Analysis, Section 7.1.2

Other Statistical Analyses
Other Endpoint
• Mean change from baseline in pre- and post- bronchodilator FEV1 at Week 32
Model Specification
• See Primary Efficacy Statistical Analysis, Section 7.1.2
Model Checking & Diagnostics
• Refer to Appendix 11: Model Checking and Diagnostics for Statistical Analyses .
Model Results Presentation

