
 Adjusted means and the corresponding 95% confidence intervals will be presented by visit The estimated adjusted means will be presented using the observed marginal distributions of the sample covariates (OM option in LSMEANS statement). The Kenward and Roger method for approximating the denominator degrees of freedom and correcting for bias in the estimated variance-covariance of the fixed effects will be used (DDMF=KR). An unstructured covariance structure for the R matrix will be used by specifying 'type=UN' on the REPEATED line. Change from the baseline at each Visit X will be calculated by (Estimated Score at Visit X minus Estimated Score at Baseline) and the corresponding 95% confidence intervals. Adjusted means at each visit will also be presented. Plots of Least Squares (LS) mean change from baseline pre- and post bronchodilator FEV1 and 95% confidence intervals from the model will be generated at each visit.
On-treatment Phase
• See Primary Efficacy Statistical Analysis, Section 7.1.2

Other Statistical Analyses
Other Endpoint
• Subject rated response to therapy at Week 32
• Clinician rated response to therapy at Week 32
Results Presentation

 • The number and percentage of subjects in each response category will be presented for each visit. • The number of subjects with a missing responses at each visit will be presented in a separate category.
--

On-treatment Phase

 • An On-Treatment “de jure” analysis will also be performed which does not consider any data collected following treatment discontinuation (see On-Treatment definition within Section 10.4).

Other Statistical Analyses

Other Endpoint

 • Mean change from baseline in Treatment Satisfaction Questionnaire for Medication (TSQM-9)

Model Specification

 • The Mean Change at Week 32 will be tested to see if it is significantly different from zero using Wilcoxon signed-rank test

Model Checking & Diagnostics

 • Check for the extreme outliers by plotting the differences between TSQM-9 at Week 32 and Baseline

Model Results Presentation

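### SAP 10.4.2 writes the visit-based On-Treatment window in the wrong order, and SAP 10.3.3 reverses its slotting condition; both are drafting errors with limited reach that should be corrected before programming

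*SAP*

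**What the plan says.** SAP 10.4.2 sorts questionnaire, lung function, eosinophil and biomarker data into three phases. Pre-Treatment is "Visit date/time ≤ First dose of mepolizumab". On-Treatment for subjects who complete is "Visit date/time < First dose of mepolizumab ≤ Visit 10 (Exit Visit)* visit date/time". For subjects who discontinue or withdraw early it begins "Visit date/time < First dose of mepolizumab ≤ Earliest of (1) Last dose of mepolizumab + 28 days", with the early withdrawal or discontinuation visit as the alternative limit. Off-Treatment is anything after the relevant limit.

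SAP 10.4.1 gives the matching rule for exacerbations in the usual order: "First dose of mepolizumab ≤ Date & time ≤ Visit 10 (Exit Visit)* visit date".

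SAP 8.1.2 describes the on-treatment analysis in words and points to 10.4 for its definition: "analysis will also be performed which does not consider any data collected following treatment discontinuation (see On-Treatment definition within Section 10.4". Note 3 of SAP Table 5 does the same: "To analyse data collected whilst On-Treatment, not considering any data collected following treatment discontinuation (see Section 10.4". That note is attached to the on-treatment rows for eosinophils, response to therapy and TSQM-9. The Biomarkers row of Table 5 does not carry it, so for biomarkers the pointer to 10.4 comes from 8.1.2 alone.

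On slotting, SAP 10.3.2 moves early-withdrawal data to the nearest suitable visit when nothing was recorded there. SAP 10.3.3 says it applies similar logic to unscheduled visits, but makes existing data at the scheduled visit the condition for slotting. Its next sentence keeps an unscheduled value out of by-visit summaries and analyses when both neighbouring visits have data. SAP 10.5.3 repeats that second rule and refers back to 10.3.

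**The concern.** An analysis plan is also a programming specification. Where 8.1.2 and Table 5 send the reader to 10.4, the definition found for visit-based data is 10.4.2. Coded as written, the on-treatment set would hold only pre-dose records, and the tables that depend on it would show no post-dose results. A programmer who notices must depart from the written rule.

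The slotting condition raises a similar problem. Coded as written, an unscheduled value could not fill an empty scheduled visit, yet could be added to an occupied one. SAP 10.6.1 averages multiple measurements at one time point for summary statistics unless a selection process is specified, so a recorded scheduled value could be altered.

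**Working it through.** **Phase rules in 10.4.2.** Inputs: the three rows of SAP 10.4.2, and visits every 28 days from Protocol 7.1 (Visit 3 = day 28, Visit 10 = 8 × 28 = day 224). Assumptions: Visit 1 at day −21; Visit 2 assessments timed just before the first dose at day 0. The order as written is visit < first dose ≤ limit. The corrected order is first dose < visit ≤ limit.

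Completer, limit = Visit 10 (day 224):

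| Visits | Day | Phases met as written | Phases met, corrected order |
|---|---|---|---|
| 1 and 2 | −21, just before 0 | Pre and On | Pre |
| 3 to 10 | 28 to 224 | none | On |

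Example discontinuer, last dose at Visit 5 (day 84), still attending visits as Protocol 5.5.1 encourages, with no earlier discontinuation visit. Limit = 84 + 28 = day 112:

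| Visits | Day | Phases met as written | Phases met, corrected order |
|---|---|---|---|
| 1 and 2 | −21, just before 0 | Pre and On | Pre |
| 3 to 6 | 28 to 112 | none | On |
| 7 to 10 | 140 to 224 | Off | Off |

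In both cases none of the eight post-dose visits is On-Treatment as written. With the corrected order every visit falls in exactly one phase. If Visit 2 and the first dose carry the same time, or only dates are compared, Visit 2 meets Pre alone; the post-dose result does not change.

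**Which displays use the rule** (SAP Table 5, 8.1.2 and 10.13.1.3): eosinophil sensitivity analysis 2.29 (1), response ratings 2.34 and 2.35 (2), TSQM-9 2.36 (1), biomarkers 2.37 to 2.46 (10). Total 1 + 2 + 1 + 10 = 14; the ten biomarker tables are one summary repeated by analyte. The amount of post-dose data behind them differs:

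- Eosinophils: all eight post-dose visits (Protocol 7.1).
- Biomarkers: two, Visits 4 and 10 (Protocol 7.5).
- TSQM-9: one, the Exit Visit (Protocol 7.1).
- Response ratings: some visits only (Protocol 7.1).

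**Which analyses do not use it.** SAP 7.1.2 includes all ACQ-5 data to Week 32 whether or not treatment continued. SAP 8.1.2 applies the same to SGRQ, FEV1 and the main eosinophil and exacerbation analyses. On-treatment exacerbation analyses use 10.4.1, which is in the right order.

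**Slotting in 10.3.3**, set against 10.3.2:

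| Closest visit | Other neighbour | 10.3.2 logic | 10.3.3 as written |
|---|---|---|---|
| empty | empty or recorded | slot | do not slot |
| recorded | empty | do not slot | slot onto the occupied visit |
| recorded | recorded | do not slot | first sentence slots, second bars use |

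In the last row the second sentence of 10.3.3 and SAP 10.5.3 lead to the same result as 10.3.2.

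**The case against.** The strongest reply is that nobody would be misled. SAP 8.1.2 defines the on-treatment analysis by exclusion, as leaving out data after treatment discontinuation. The Off row, which that exclusion needs, is correct, as is the Pre row. Taking what lies between them gives the intended set, and 10.4.1 shows the order. A window that would make all of a completer's on-treatment visits pre-dose is plainly a slip. This stands as to intent and limits the consequence: the affected tables need not come out empty. It does not make the rule right, because 8.1.2 sends the reader to 10.4 for the definition and the definition found there is inverted in two rows.

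On 10.3.3, with four-weekly visits the usual case is probably that both neighbours are recorded, and there the net result is the intended one. That also stands. Averaging can arise only when the closest visit is recorded and the other neighbour is empty.

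Three stronger readings are tempting, and the documents do not support them.

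- A reader might infer that the primary or main secondary results are at risk from 10.4.2. They use all data to Week 32 or the rule in 10.4.1.
- A reader might infer from the word also in 8.1.2, and from the unrestricted TSQM-9 test specification ("The Mean Change at Week 32 will be tested to see if it is significantly different from zero using Wilcoxon signed-rank test"), that the dataset for that test is undefined or that all-data versions of 13 tables (14 less 2.29, which has 2.28) are missing. Table 5 gives the entry "Treatment Satisfaction Questionnaire for Medication (TSQM-9" only an on-treatment row, 8.1.2 places the p-value in the table, and the only TSQM-9 table listed is 2.36, titled as on-treatment only. The documents largely settle this.
- A reader might take the eight unclassified visits of a completer as data lost, or the mismatched slotting cases as a frequency. Both describe the rules. TSQM-9 has a single post-dose assessment and biomarkers have two.

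**Conclusion.** Both rules are wrong as written and should be corrected, though neither threatens the main conclusions. Under 10.4.2 no post-dose visit is On-Treatment, and post-dose visits inside the window have no phase. The consequence is confined to one eosinophil sensitivity table, two rating tables, one TSQM-9 table and ten biomarker summaries. The intent is recoverable without a judgement call.

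The 10.3.3 reversal is a separate and probably smaller matter. The unscheduled assessments the protocol provides for are repeat laboratory tests (7.4.7), a blood count after a liver event (Appendix 5) and extra ECGs (5.5.4, 7.4.6); it makes no provision for unscheduled ACQ-5 or SGRQ. The documents give no expected number of unscheduled assessments, so the effect cannot be sized.

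The phase check assumes nominal visit days and pre-dose timing of Visit 2. It also takes the inequality signs as they appear in the PDF text. The same order in two separate rows, beside correctly ordered neighbours, makes a conversion artefact unlikely.

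**What to change.** In SAP 10.4.2, write both On-Treatment rows as First dose of mepolizumab < Visit date/time ≤ the existing upper limit. This fits the Pre and Off rows without changing them.

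In SAP 10.3.3, allow slotting only if no information already exists at the scheduled visit. Otherwise the value stays in the unscheduled visit, as the second sentence of 10.3.3 and SAP 10.5.3 already provide.

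The cost is a few words of SAP text before programming. No new data, displays or analyses are needed.
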